#### **9.3.4. Initial home visit: Home built environment audit (caregiver)**

Before the home environment audit can begin, study personnel will obtain permission from a full-time resident of the household for which measurements are requested. The PresPA Study Consent Form (B) allows for photography to be used to capture the built physical environment of the home. Once consent is provided, the home audit can begin. If the owner of the home refuses to sign Consent Form (B), the home built environment audit will still proceed; however, no photography will be conducted in the home. The participant and their caregiver are still eligible to participate in all other study procedures, with the exception of the collection of photographs.

Once consent has been given, study personnel will ask the caregiver if there are any restricted areas within the indoor home environment where their child is not allowed access. These areas will not be included in total available floor space ( $m^2$ ) of the indoor space. The study personnel will then draw the layout of the indoor space (Form 3). Then, using a laser measuring device (Disto™ D1, Leica Geosystems, Switzerland), the study personnel will measure the dimensions of the space, collecting measures in duplicate. They will include any furniture that is greater than  $1 m^2$ , including each piece of furniture in the drawing of layout, as well as measuring the dimensions of furniture in duplicate using a standard tape measure. Study personnel will not include any beds or sofas in the drawings, as they will not be subtracted from the available indoor floor space (since it is common for children to use beds or sofas as a play space in Dhaka). They will also be asked to take at least 2 photographs of each room within the home, consent permitting, to accompany the area measurements. These pictures will not include any individuals and will strictly capture the physical built environment of the indoor space.

Next, the study personnel will ask about any outdoor spaces that are accessible to the child. Only outdoor spaces that have clear perimeters (e.g., fenced in backyard, railings or walls surrounding a rooftop, railings surrounding a balcony) will be measured using the laser-measuring device. If the laser does not operate in the outdoor environment (e.g., weather conditions do not permit the proper lighting standards necessary to obtain a reading), a standard tape measure will be used. Open streets, alleyways, large parks or green spaces, or outdoor spaces that do not have a clear perimeter will not be measured; however, they will be documented and physical characteristics will be described by study personnel in the

appropriate sections of Form 3. Study personnel will be asked to photograph all outdoor spaces, consent permitting, as long as they do not include any individuals within the pictures.

Once the indoor, and if applicable, outdoor area has been measured, the study personnel will assess the home environment for physical hazards. Using the audit provided (Form 3), they will assess the presence and safety surrounding stairwells, accessibility to stovetops and open sewage drains, as well as the presence of unfinished construction and common household hazards (e.g., boti, a common household cutting device in Bangladesh). A check list will be provided to the caregiver at the final visit which will indicate if any of the 5 hazards that we are assessing are present in their home. In addition, we will provide them with strategies to increase safety of their children (e.g., put up railing around stairwells, keep boti in a space that isn't accessible to the child, etc.).

Finally, study personnel will take an inventory of any gross-motor activity-facilitating items within the home (Form 3). They will ask the caregiver to show/bring them items with which they allow their child to play on/with. Study personnel will then document each item on the audit form (Form 3) and take photographs of each item (up to 10 items). These photographs will not include individuals, but will strictly capture the gross-motor activity-facilitating items present in the home. During data input, the student investigator will evaluate these items and place them into specific categories: fine-motor activity item, stationary/fixed gross-motor activity item, portable gross-motor activity item (ball play equipment, push/pull equipment, riding equipment, rocking and twisting equipment) .

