Total number of stationary gross-motor activity items	Count (all integers between 0 and 10); discrete	
Data required:
 
 
• Form 3: Questions 17b-c, 18b-c, 19b-c, 20b-c, 21b-c, 22b-c, 23b-c, 24b-c, 25b-c, 26b-c
 
• The number of incidences where both the 'b' question = 2 AND the 'c' section = 2 (e.g., 17b = 2 AND 17c = 2, this indicates that this item is a stationary gross-motor activity item)
 
 
The number of items that satisfy the above rules will be added together to provide this score. The minimum score is 0 items, with a maximum score of 10 items.

Total number of portable gross-motor activity items	Count (all integers between 0 and 10); discrete	
Data required:
 
 
• Form 3: Questions 17b-c, 18b-c, 19b-c, 20b-c, 21b-c, 22b-c, 23b-c, 24b-c, 25b-c, 26b-c
 
• The number of incidences where both the 'b' question = 1 AND the 'c' section = 2 (e.g., 17b = 1 AND 17c = 2, this indicates that this item is a portable gross-motor activity item)
 
 
The number of items that satisfy the above rules will be added together to provide this score. The minimum score is 0 items, with a maximum score of 10 items.

Hemoglobin concentration	g/L; continuous	Hemoglobin concentration data collecting in Form 4: Q24.

Table 2 - List of additional continuous covariates and their derivation

Variable	Unit	Derivation
Body mass index (BMI) (caregiver)	kg/m 	
Data required (Form 2: Q10-13):
 
 
• Height (m; average of 2 closest height measures)
 
• Weight (kg; average of 2 closest weight measures)
 
 
BMI will be calculated using the formula:  <math>BMI = \text{weight}/\text{height}^2</math>

Body mass index (BMI) z-score (child participant)
	
(z-score)
	
Data required (Form 2: Q1-4):
 
 
• Height (m; average of 2 closest height measures, value will be adjusted by subtracting 0.7 cm if recumbent length was measured)
 
• Weight (kg; average of 2 closest weight measures)
 
 
Height and weight will be plotted on the WHO body mass index-for-age (BMI-for-age) chart (sex specific; ages 2 to 5 years) to determine participant BMI z-score.

Waist circumference
	
cm
	
Average of the 2 closest waist circumference measures (Form 2: Q5,6,14,15)

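### Both gross-motor item counts are taken from the same ten Form 3 slots, which as written also hold fine-motor items, so they can be too low, without any flag, in homes that show more than ten items

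*Combined protocol and SAP*

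**What the plan says.** **Collection (section 9.3.4).** The stated target is gross-motor items: "study personnel will take an inventory of any gross-motor activity-facilitating items within the home (Form 3"). The request to the caregiver is wider: "They will ask the caregiver to show/bring them items with which they allow their child to play on/with". Recording follows: "Study personnel will then document each item on the audit form (Form 3) and take photographs of each item (up to 10 items"). Sorting is placed later, and fine-motor is one of the classes: "During data input, the student investigator will evaluate these items and place them into specific categories: fine-motor activity item". Stationary and portable gross-motor are the others.

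**Derivation (section 17, Table 1).** The stationary and portable counts list the same source: "Form 3: Questions 17b-c, 18b-c, 19b-c, 20b-c, 21b-c, 22b-c, 23b-c, 24b-c, 25b-c, 26b-c". The stationary rule is "The number of incidences where both the 'b' question = 2 AND the 'c' section = 2"; the portable rule is "The number of incidences where both the 'b' question = 1 AND the 'c' section = 2". For each count, "The minimum score is 0 items, with a maximum score of 10 items".

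**Use.** Section 10.4.1 names the stationary and portable counts among the Objective 2 exposures, to be related to counts per 15 seconds in a mixed linear model. Section 10.2 also lists a fine-motor item count as an exposure and refers to Table 1 for derivations, but Table 1 has no entry for it. The sensitivity analyses in section 10.4.2 do not mention the item inventory.

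**The concern.** Read alone, section 9.3.4 could be limiting only the photographs to ten. Table 1 shows that the limit also reaches the analysis data, because the two counts can draw on ten item records and no more. Nothing reserves those records for gross-motor items. The plan gives no order of listing, does not ask for the total number shown, and mentions neither a continuation sheet nor a truncation flag.

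The loss can occur only in homes with many items, so the measurement error depends on the exposure itself. It is not random noise around a correct count. With a target of about 60 children, a few truncated homes at the upper end of the range could carry high leverage on the slope. Items left off the form at the visit cannot be recovered from the forms afterwards.

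**Working it through.** **1. The plan's own maximum.** Q17 to Q26 is 26 − 17 + 1 = 10 slots, one item each. This reproduces the stated maximum of 10.

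**2. The limit is joint.** A slot adds to a gross-motor count only if c = 2, with b separating stationary from portable. The c condition would be unnecessary if every slot held a gross-motor item. So, as written,

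stationary + portable + fine-motor ≤ 10.

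If 7 slots hold fine-motor items, at most 10 − 7 = 3 remain for both gross-motor counts together.

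**3. Expected loss in one home.** Let T be the items shown and g the gross-motor items among them. For T > 10:

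- Random order: each item has probability 10/T of being listed, so the expected recorded count is g × 10/T and the proportional loss is 1 − 10/T.
- Fine-motor items first: max(0, 10 − (T − g)).
- Gross-motor items first: min(g, 10).

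The documents give neither T nor g. The values below are assumptions, with g = 5.

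| T | Random order | Loss | Fine-motor first | Gross-motor first |
|---|---|---|---|---|
| 10 or fewer | 5.0 | 0% | 5 | 5 |
| 12 | 5 × 10/12 = 4.2 | 17% | 10 − 7 = 3 | 5 |
| 15 | 5 × 10/15 = 3.3 | 33% | 10 − 10 = 0 | 5 |
| 20 | 5 × 10/20 = 2.5 | 50% | 0 | 5 |
| 30 | 5 × 10/30 = 1.7 | 67% | 0 | 5 |

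**4. Effect on a slope (illustration only).** Item totals were simulated from a negative binomial distribution (shape 3) with mean 5, 8, 12 or 20. The gross-motor share was 30% or 50%, listing order was random, the outcome SD was 9.7 cp15s (section 9.6), and the true slope was 1.0 per gross-motor item. Stationary and portable items were pooled.

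| Assumed mean items | Homes above ten | Correlation, recorded with true count | Estimated slope |
|---|---|---|---|
| 5 | 8% | 0.96 | 1.08 to 1.11 |
| 8 | 27% | 0.85 to 0.86 | 1.21 to 1.28 |
| 12 | 50% | 0.70 to 0.71 | 1.29 to 1.52 |
| 20 | 76% | 0.45 to 0.47 | 1.34 to 1.66 |

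Under random order the per-item slope is inflated, because high true counts are compressed into a shorter recorded range. If fine-motor items tended to be listed first, the ranking of homes could be blurred or even reversed.

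**The case against.** Several arguments on the other side have force.

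- **The cap may rarely bind.** The setting is described as resource-poor, and the study's hypothesis concerns a lack of play-oriented features in the home. At the mild end of the simulation (8% of homes above ten, correlation 0.96, slope 1.08) the effect is small. This stands: the documents cannot show that the cap binds often, or at all.
- **Staff know the target.** Section 9.3.4 opens by naming gross-motor items and says the photographs are to capture those items. A reader might infer from the later sorting that staff cannot give these items priority. The text does not support that; staff can recognise a ball or a ride-on toy. What remains is that no instruction tells them to list such items first.
- **Form 3 is not in the documents.** Table 1 treats b and c as Form 3 questions, which might be answered at the visit, whereas section 9.3.4 places categorisation at data input. A continuation sheet may exist. That the fine-motor count comes from the same slots is an inference, because Table 1 gives no source for it. This limits certainty, but the written plan still gives no rule for an eleventh item.
- **Less sensitive codings exist.** Section 10.2 uses presence of gross-motor items by category, and section 10.4.1 allows discrete variables to be categorised. Both are less affected by a ceiling. The counts nevertheless remain named Objective 2 exposures.
- **The 0 to 10 ranges.** A reader might take these as an error in Table 1. They are not: either count alone can run from 0 to 10, and the joint ceiling does not contradict that.

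**Conclusion.** The point holds as a conditional weakness in how an exposure is measured. Both gross-motor counts share ten slots with fine-motor items as the plan is written, no listing rule covers homes above ten, and full forms are not treated as truncated. A gross-motor count is too low only if a home shows more than ten items and a gross-motor item is among those left out. Under random listing the expected loss is then 1 − 10/T: 33% at 15 items and 50% at 20. There is none at ten or fewer, and none if staff list gross-motor items first and there are no more than ten of them.

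Three stronger readings are tempting and go beyond the documents:

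- That homes with many toys are in fact under-counted. No distribution of item numbers is given, and the affected homes may be few.
- That the form forces a negative relation between fine-motor and gross-motor counts in general. It does so only among homes whose ten slots are all filled; below ten the counts are unconstrained.
- That the bias runs towards the null. In the illustration it ran the other way, and the direction depends on listing order.

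**What to change.** **Collection.** Apply the ten-item limit to photographs only. Have staff ask for and list all gross-motor items first, without a cap, then fine-motor items, and record whether the list was cut short. State the source of the fine-motor count in Table 1.

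**Homes already audited.** Report how many have all ten slots full. This needs no new data and puts an upper limit on the number of homes affected. Treat the gross-motor counts in those homes as possibly truncated, that is, as lower bounds. Repeat the Objective 2 model as a sensitivity analysis with those homes flagged or with the count categorised under a top category, and also with them excluded. Exclusion should not stand alone: it drops homes with exactly ten items, which are measured correctly, and it removes the top of the exposure range.

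**Cost.** A small change to the form and instructions, a few extra minutes in some homes, and one or two extra model runs. Version 1.4 is dated April 2018 and the study is planned to end in August 2018, so a form change may come late. If the form changes mid-study, two recording methods would be mixed and the model would need a form-version indicator. If audits are complete, only the analysis part applies.

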### **9.3.5. Accelerometry & Global Positioning System (GPS) logging (child)**

At the end of the initial home visit, the study personnel will provide the participant with their activity belt. The belt will consist of a tri-axial accelerometer (ActiGraph GT3X-BT, ActiGraph Corp., Pensacola, FL, USA) that will be positioned at the right hip, and a passive GPS logger (iTrail H6000, KJB Security Products Inc., TN, USA) that will be either positioned at the left hip of the child, or on the arm of the caregiver. The placement of the GPS logging device will depend on the participant's comfortability with wearing the device on the activity belt, otherwise it is acceptable for the caregiver to wear it on their person. Both the accelerometer and GPS logger will be charged and initialized prior to the home visit. The study personnel will then provide the caregiver with instructions on how the belt is positioned on the child and explain that the child is to wear the belt 24 hours each day. The belt should only be removed during periods of bathing and swimming. As mentioned above, to improve child comfort during the day or while sleeping, the caregiver may remove the GPS device from the pouch attached to the belt at anytime and wear it on their person (a separate, additional belt will be provided to the

caregiver during the initial home visit), so long as they are with their children at all times during the day. Caregivers can remove the belt while sleeping if they find it uncomfortable, but must reattach it each morning.

The accelerometer will objectively measure all movement of the device-wearer continuously. The device is to be worn continuously for 7 days; however, the child can wear the device for 7 days non-consecutively within a 14-day time period if the caregiver identifies that the child is travelling away from home, is ill (e.g., illness that parent perceives as greatly affecting PA, such as fever, major injury, etc.), bedridden, or hospitalized. Accelerometry and GPS data will not be included in analyses during those specified days. This will continue until the caregiver indicates that the participant has returned home from travelling or is no longer ill, bedridden, or hospitalized, when accelerometry collection can resume. Study personnel will gather this information via the daily telephone calls with the participant's caregiver (section 9.3.6).

The accelerometer device will be set to collect data at 30 Hz (i.e., it will take readings 30 times per second) to ensure high-quality data. Data can only be viewed after the device has been collected from the participant and uploaded into the software program (ActiLife v10). Activity is measured in counts, and is analyzed over specified time periods. Once the number of counts has been analyzed over a specified time period, the data point is then referred to as an 'epoch'. Data will be analyzed in 15 second epochs (counts per 15 seconds; cp15s).

The GPS logger will objectively measure the coordinates of each location that the participant travels. As with the accelerometer, the GPS logger device is to be worn continuously for 7 days, or non-consecutively within a 14-day time period. The collection of location data will occur simultaneous to the collection of accelerometry data. To ensure quality location data, the device will be set to take readings every 15 seconds, as this will directly correspond to the 15 second epochs calculated from the processed accelerometry data. This data will be used in combination with the accelerometry data to gain insight on the location of preschooler activity (e.g., home, park, relative's home, street, etc.). Similarly, as with the accelerometry data, data collected from the GPS logger can only be viewed after the device has been collected from the participant and downloaded into the software program (iTrail GPS Mapping and Trip Analysis Software). This passive GPS device does not offer remote real-time tracking; therefore, it cannot provide real-time location data and data can only be collected once the device has been returned.

The data collected from the GPS logger in combination with the accelerometry data will substantially increase the measured accuracy, sensitivity and objectivity of an individual's exposure to environments while they engage in active behaviour. Together, the will

objectively, and accurately, measure the types of environments that individuals are exposed to, the duration they were there for, and what kind of active behaviours they participated in .

The combination of accelerometers and GPS logging devices have been used in a few studies that measure the risk factors surround PA of preschool-aged children specifically . Each of these studies utilizes an activity belt system on which we have modeled our design (e.g., accelerometer positioned on the right hip; GPS logger positioned on the left hip).

### **9.3.6. Daily phone calls (caregiver)**

Every afternoon, study personnel will call the caregiver and go through a daily recall of (a) what time the participant woke up in the morning, (b) if, and when, the activity belt was removed during the participant's waking hours, (c) what time the participant went to sleep, and (d) if the participant left the home during the day (including location and duration away from home). This information will be documented in the Accelerometry & GPS Log each day. If a participant's caregiver cannot be reached on any particular day, study personnel will attempt to call 2 additional times that day. If contact has not been made, study personnel will contact the participant's caregiver the next morning and ask them to recall the previous day, then call again in the afternoon to recall the current day; a normal calling schedule will resume. If contact has not been made within 3 days, which has not been previously agreed upon between the participant's caregiver and study personnel (e.g., the participant is travelling, sick, etc.), the participant will be removed from the study and study personnel will visit the participant's home to collect the activity belt.

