We will use the cut-points established by Trost and colleagues:  $\leq 48$  cp15s for sedentary behaviour (SED), 49-418 cp15s for light physical activity (LPA), and  $>418$  cp15s for moderate-to-vigorous physical activity (MVPA) . These cut-points were chosen because they were derived from direct observation of a sample of toddler and preschool-aged children while wearing the ActiGraph GT1M accelerometer . Videos of the children playing were coded using a modified version of the Children's Activity Rating Scale before receiver operating characteristic curve analyses were conducted to determine the corresponding cut-points to the 3 categories of interest: SED, LPA, and MVPA . These results were found to exhibit excellent classification accuracy . They were then cross-validated against pre-existing cut-points that are established for toddlers and preschoolers, which were not found to be significantly different than the pre-established cut points established by Pate and colleagues  and those established by National Health and Nutrition Examination Survey .

We will then be able to calculate total time (minutes) as well as proportion of time (%) spent in each activity category (SED, LPA, MVPA). The overall mean cp15s for each child will be based on all 15-second epochs that occurred during eligible wear periods from the time that the caregiver indicated the child woke up until the time that the caregiver indicated the child went to sleep at. If this data is missing, we will use eligible wear periods between 8am to 8pm. This mean will exclude non-wear periods as defined above and when the accelerometer was not being worn by the child (based on daily logs collected from the caregivers via afternoon telephone call; Section 9.3.7.).

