We will then estimate the frequency of children who met Canadian physical activity 24 Hour Movement Guidelines recommendations on any day, and the average number of days on which children met the recommendations for sleep duration (10-13 hours/day). Bangladeshi recommended guidelines for preschool-aged children will be used if they are available at the

time of statistical analyses. These data will be compared to published results in similar international, preschooler populations.

This will be done using the same data files collected from the participant; however, we will only use data from non-waking hours. We will use the ActiLife software to analyze all nighttime activity data and derive variables pertaining to sleep quantity and quality.

We will also compare objectively measured sleep periods (based on accelerometry) with parent reported bedtimes and waking times. This will be done using Individual Manual Inspection (IMI) by comparing bedtimes and waking times reported in the Accelerometry & GPS Log to the computed activity and sleep graphs created in the ActiLife software.

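### On routinely reached days the caregiver is called before the bedtime and evening that the call must record, and that bedtime closes the primary-outcome window

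*Combined protocol and SAP*

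**What the plan says.** Section 9.3.6 (Daily phone calls) fixes both timing and content. On timing: "Every afternoon, study personnel will call the caregiver and go through a daily recall of (a) what time the participant woke up in the morning". The second item is "b) if, and when, the activity belt was removed during the participant's waking hours". The third and fourth, on bedtime and outings, read in part "c) what time the participant went to sleep, and (d) if the participant left the home during the day (including location and duration away from".

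The day covered follows from the missed-call procedure. If no contact is made, "study personnel will contact the participant's caregiver the next morning and ask them to recall the previous day". For the rest of that following day, the instruction is: "then call again in the afternoon to recall the current day; a normal calling schedule will resume". So the ordinary afternoon call concerns the current day, and only a day with failed contact is recalled the next morning.

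Section 10.1 (Outcome measure) builds each child's mean cp15s from epochs between the reported wake time and the reported bedtime: "until the time that the caregiver indicated the child went to sleep at. If this data is missing, we will use eligible wear periods between" (the fallback runs from 8 am to 8 pm). It excludes belt-off time using the logs from these calls (citing section 9.3.7, although the calls are in 9.3.6). It applies the same window to the 600-minute valid-day rule and takes indoor wear time from maternal report. Section 10.4.1, Objective #4, also compares measured sleep with parental report by "comparing bedtimes and waking times reported in the Accelerometry & GPS Log".

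**The concern.** A recall can only describe what has already happened. An afternoon call about the current day comes before that day's bedtime and before any evening belt removal or outing. The bedtime field can then hold one of three things: a forecast, nothing, or the bedtime of the night before. Section 9.3.6 does not say which is wanted, and no section assigns a previous-night bedtime to the previous day's record.

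The consequences differ by case. A bedtime logged too late admits sleep epochs to the waking mean. One logged too early cuts evening play. A missing one invokes the 8 am to 8 pm window. Minutes and proportions in each activity category and the valid-day decision use the same window, so they are affected too. The Objective #4 comparison loses its meaning if the reported time is a forecast or belongs to another night. In section 10.4.2, where parental location reports are checked against GPS, an evening outing that nobody asked about would look like a parental omission.

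**Working it through.** **The plan's own figure.** Section 9.6 gives ±2.45 cp15s for n = 60 and SD 9.7. At the 95% level used for Objective #1: 1.96 × 9.7 / √60 = 2.454. It reproduces, and this point does not depend on it.

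**Timing check, item by item, for a routinely reached day.**
- Wake time: already past at the call, so reportable.
- Belt removals and outings: reportable up to the call. Section 9.3.6 does not say that the next call asks about the rest of the day.
- Bedtime: not yet reached.
- Last worn evening: section 9.3.7 arranges the final visit once the caregiver says that the 7 days are complete, but neither it nor section 9.3.9 states a recall of that evening.
- Missed-contact day: recalled the next morning, so the whole day is covered. Log completeness therefore differs between reached and missed days.

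**How much of the day follows the call.** The documents give neither call hour nor typical bedtime, so both are assumed.

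Share of the 08:00–20:00 window after the call = (20:00 − call) / 12 h:
- 12:00 call: 480 min, 67%
- 15:00 call: 300 min, 42%
- 17:00 call: 180 min, 25%
- 18:00 call: 120 min, 17%

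With waking at 08:00 and bedtime at 21:00–23:00, share after the call = (bedtime − call) / (bedtime − 08:00):
- 15:00 call: 6/13 to 8/15, or 46% to 53%
- 17:00 call: 4/13 to 6/15, or 31% to 40%

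**Against the 600-minute rule.** The period before the call reaches 600 minutes only if the child woke at least 10 hours earlier: by 02:00, 05:00, 07:00 or 08:00 for calls at 12:00, 15:00, 17:00 or 18:00. Otherwise, counting a day as valid needs evening hours that the call has not covered.

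**What the fallback leaves out.** With waking at 08:00 and bedtime at 21:00–23:00, stopping at 20:00 omits 60/780 to 180/900 minutes, or 8% to 20% of the waking day.

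**Illustrative shift in one child's mean.** Suppose k minutes of restless sleep at 10 cp15s, not removed as non-wear, enter a 720-minute record with true mean M. Shift = (720M + 10k)/(720 + k) − M = k(10 − M)/(720 + k).
- M = 50: k = 20 gives −1.1; k = 60 gives −3.1
- M = 150: k = 20 gives −3.8; k = 60 gives −10.8

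All values of M, k and the sleep count are assumptions. The result concerns one child with a bedtime logged too late.

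**The case against.** The bedtime item is in the past tense and is asked alongside the morning wake time. A caregiver phoned in the afternoon might well give last night's bedtime, and daily calls would then yield a bedtime for each earlier night. The Accelerometry & GPS Log is not reproduced, so its fields may be fuller than the summary in section 9.3.6. The arrangement of the final visit shows that contact after the last worn day is possible. Several backstops exist:
- Runs of at least 20 minutes of zero counts are removed by algorithm. This catches long removals and still sleep, including nights when the belt comes off for sleep, as section 9.3.5 allows.
- A missing bedtime has the 8 am to 8 pm window.
- GPS supplements the report for time in or around the home.

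Much of this stands. A reader might infer that evening events can never be reported. That is too strong: missed-contact days are recalled whole, and last night's bedtime may be given. A reader might also infer that unlogged evenings are counted as time at home, but no section states such a default.

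The scheduling problem remains. No section says that the item means last night, or dates it to the previous day. The backstops do not supply a bedtime, and the fallback does not catch a forecast or wrongly dated one. Removals shorter than 20 minutes can escape the algorithm. Indoor wear time rests on maternal report alone. The GPS unit may be carried by the caregiver (section 9.3.5) or taken out of its pouch at undisclosed locations (section 13).

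**Conclusion.** The point holds for routinely reached days. As written, the call comes before the bedtime and evening that it must document, and that bedtime delimits the primary outcome, the valid-day rule and the sleep comparison. This is a conflict between the call schedule and the use made of its answers, so it goes beyond a missing detail. It merits correction because the primary outcome depends on it and the repair is small.

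The size and direction of any bias cannot be computed from the documents. Two stronger readings are tempting and unsupported:
- The 17% to 67% shares are not data loss. The accelerometer records throughout, and only the caregiver's annotation is affected.
- The shifts of −1.1 to −10.8 cp15s should not be set against the ±2.45 margin. They are per-child figures under assumed inputs, whereas the margin is for the mean of 60 children. The two are comparable only if errors run the same way across children and days, which nothing in the plan establishes. Previous-night bedtimes could err in either direction.

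**What to change.** In section 9.3.6, make each call cover the interval since the previous call: removals and outings since then, last night's bedtime entered against the previous day's record, this morning's wake time, then today so far. Collect the last worn evening at a short closing contact or at the final visit. Alternatively, make the next-morning recall of the whole previous day, already used after missed calls, the standard call.

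In section 10.1, state which night each logged bedtime denotes and which window applies when only the bedtime is missing. Correct the cross-reference to the calls from 9.3.7 to 9.3.6. For any data already collected, the same statement should say how the logged bedtimes were understood and how evenings without a recall are handled.

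The cost is a reworded script and log and one added closing question, with the same staff. The drawback is that the evening is recalled the next day.
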